9.7.3.1. Incidence Rates of AESIs in Subgroups of Patients

If data are available and appropriate predictors are available in the respective database, sensitivity analyses around the definition of each type of AESI will be performed. Incidence proportion and density of each type of AESI will also be calculated for the subgroup of patients compliant or non-compliant with the EU SmPC (as listed in section 9.7.1, the criteria will be adapted for the relevant country of the data source stems if the SmPC differ across such countries, i.e., for U.S.), including relevant comorbidities, concomitant medications, and pregnancy. Adaptations will be made if BMI is not available; these will be described in the SAP. The incidence rate (and 95% CI) of new onset comorbidities and concomitant medication after initiation of Mysimba/Contrave will be assessed. Incidence rates will be determined both for the person-years of time exposed to Mysimba/Contrave (i.e., while patient taking medication) after the index date as well as for all person time through 548 days after the index Mysimba/Contrave prescription.

The incidence rate (and 95% CI) of pregnancy and breastfeeding after the Mysimba/Contrave index date will be assessed among females initiating Mysimba/Contrave. These analyses will be conducted in data sources where the necessary variables are present.

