characterize the safety profile of Mysimba. As a supplement to the Mysimba Risk Management Plan (RMP), Orexigen has designed this database study to address that request. This study will describe the utilization and safety of Mysimba/Contrave in a real-world setting using electronic health records (EHR) and administrative health claims in several European countries and the U.S. Available characteristics of patients initiating Mysimba/Contrave will be described, with particular focus on patients receiving Mysimba/Contrave in a manner noncompliant with the Summary of Product Characteristics (SmPC) at initiation, such as use inconsistent with labelled indication or use in patients with a contraindication to the medication. Use inconsistent with labelled or otherwise authorized indication includes, but is not limited to: age <18 years and use for a reason other than management of weight in a patient who has obesity or is overweight. Contraindications include, but are not limited to, the following: current diagnosis of uncontrolled hypertension, seizure disorder, or end-stage renal failure; history of seizures, bipolar disorder, anorexia nervosa or bulimia; current dependence on chronic opioids or opiate agonists (e.g., methadone); current state of acute opiate withdrawal; or any concomitant treatment containing bupropion, naltrexone, or a monoamine oxidase inhibitor (MAOI). This study also plans to evaluate the incidence of adverse events of special interest (AESI) in real-world settings. The incidence of seizures, suicidality (i.e., suicidal ideation, attempted

Mysimba/Contrave, to inform the MAH's view on the following:To further refine the risk management and pharmacovigilance planning for this product;

suicide or completed suicide), neuropsychiatric events (i.e., mania or depression), hepatotoxicity,

or severe hypersensitivity reactions following initiation of treatment with Mysimba/Contrave

will be investigated. Additionally, the incidence of AESIs will be evaluated in subgroups of

Results from this study will add further definition and clarity to the overall safety profile of

patients, including those who do not adhere to the conditions of use set out in the SmPC.

2. To determine whether the SmPC should be revised, based on the available post-marketing evidence, with the objective of optimizing the safe and effective use of the product.

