8. RESEARCH QUESTIONS AND OBJECTIVES

The aim of the study is to assess the long-term (548 days) real-world utilization patterns of Mysimba/Contrave use among patients who are prescribed Mysimba/Contrave. There are no a priori hypotheses for this study.

The primary objectives of the study are:

- To describe demographic and baseline characteristics of patients initiating use of Mysimba/Contrave; and
- 2. To evaluate patterns of Mysimba/Contrave initiation and use, including number of prescriptions, number of treatment episodes and duration between prescriptions, as well as estimating the number and percentage of patients compliant and non-compliant with the SmPC.

Analysis of compliance to the labelled indication and contraindications will be adapted to the specific SmPC for the country relevant to the data source (s). Examples of non-compliance include, but are not limited to:

Use inconsistent with labelled indication:

- 1. Age <18 years
- 2. Use other than management of weight
- 3. Management of weight in a patient who does not have obesity or is not overweight and has a weight-related comorbidity
- 4. A prescribed maintenance dose other than the Mysimba/Contrave 32mg/360mg
- 5. Continued use past 16 weeks without \geq 5% weight loss

Use in patients with contraindications:

- 6. A current diagnosis of uncontrolled hypertension, seizure disorder (or history of seizures), or end-stage renal failure
- 7. A history of bipolar disorder, anorexia nervosa or bulimia
- 8. A current dependence on chronic opioids or opiate agonists (e.g., methadone)
- 9. A current state of acute opiate withdrawal
- 10. Any concomitant treatment containing bupropion, naltrexone, or a MAOI
- 11. Patients with a known central nervous system tumour

Proprietary and Confidential:

- 12. Patients undergoing acute alcohol or benzodiazepine withdrawal
- 13. Patients with severe hepatic impairment (dependent on local SmPC)

The secondary objectives of this study are:

- 1. To assess and compare the observed incidence of AESIs in usual clinical practice among users of Mysimba/Contrave compliant and non-compliant with the SmPC. AESIs include new onset of the following:
 - 1. Seizures
 - 2. Suicidality (i.e., suicidal ideation, attempted suicide or completed suicide)
 - 3. Neuropsychiatric events (i.e., mania or depression)
 - 4. Hepatotoxicity
 - 5. Severe hypersensitivity reaction
 - 6. Serotonin syndrome

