9.3.2. Outcomes

When available, the following variables will be collected after initiation of Mysimba/Contrave (Post-Index Date). A draft listing of variables available in each country is included in Appendix 3 and will be included as final in the Statistical Analysis Plan (SAP).

Proprietary and Confidential:

This document cannot be used, distributed, or reproduced in any way without the prior written consent of Currax Pharmaceuticals LLC.

- 1. BMI, height, and weight prior to index date, the date of initiation of the medication(s) of interest, (obtained directly from data sources; BMI may be calculated if height and weight available). In the event that BMI and/or weight are not available through licensed access to the Scandinavian National Patient Registries, an attempt will be made to identify the obese population through diagnosis codes or procedures such as counseling for weight loss. It should be noted that this approach may identify a more obese and more motivated population than what would be identified on the basis of BMI. In addition, an approach may be implemented to predict BMI or apply published algorithms predicting BMI. Details will be laid out in the SAP.
- 2. Weight will be obtained if available 16-24 weeks post-index date to evaluate use inconsistent with labelled indication. BMI after index date will be obtained in the same timeframe, if available.
- 3. Relevant comorbidities (obtained via ICD-10 codes):
 - 1. Weight-related comorbidities (i.e., type 2 diabetes, dyslipidaemia, hypertension)
 - 2. Neuropsychiatric conditions (mania, bipolar disorder, major depressive disorder [MDD], anorexia nervosa, bulimia)
 - 3. Uncontrolled hypertension
 - 4. Moderate or severe renal impairment
 - 5. End-stage renal disease
 - 6. Seizure disorder
 - 7. Hepatic impairment (defined by Child-Pugh score category)
 - 8. Central nervous system tumour
- 4. Concomitant medication use, including: naltrexone, bupropion, CYP2B6 inhibitors, CYP2B6 inducers, CYP2B6 substrates, CYP2D6 substrates, drugs that lower seizure threshold, opioid or opiate agonist, or MAOI (obtained via ATC [outpatient, Nordic data] or NDC [US data])
- 5. Pregnancy status and breastfeeding status (obtained via ICD-10 codes)
- 6. AESIs (obtained via ICD-10 codes):
 - 1. Seizures

- 2. Suicidality (i.e., suicidal ideation, attempted suicide or completed suicide)
- 3. Neuropsychiatric events (i.e., mania or depression)
- 4. Hepatotoxicity
- 5. Severe hypersensitivity reaction

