9.7.2. Descriptive Statistics

For demographic and baseline variables and duration of Mysimba/Contrave use (measured as both continuous treatment of the initial Mysimba/Contrave duration and the total treatment duration of Mysimba/Contrave), descriptive statistics will be used to describe continuous variables, (e.g., mean, standard deviation, median, quartiles 1 and 3, minimum, maximum, and two-sided 95% confidence intervals [CI]). Categorical variables will be described by the total and percentage of each response and the number of missing data (data that are unavailable in the database).

Patterns of Mysimba/Contrave use will be described by mean (standard deviation, SD) and median (quartile1, quartile 3) number of prescriptions per patient, number and duration of treatment episodes per patient as well as the average duration between prescription episodes. Analyses will be performed for all users of Mysimba/Contrave, including an assessment of whether the subjects have adhered to the prescribed treatment with Mysimba/Contrave according to the terms of the SmPC (adapted to the local country SmPC for the data source as needed, and adapted if BMI is not accessible). The number and proportion of patients who received treatment with Mysimba/Contrave will be provided according to the following subgroups (availability of variables to be summarized in SAP):

(a) Inconsistent with labelled indication:

- 1) Age < 18 years
- 2) Use other than management of weight
- 3) Management of weight in a patient who does not have obesity or is not overweight and has a weight-related comorbidity
- 4) A prescribed maintenance dose other than the Mysimba/Contrave 32mg/360mg
- 5) Continued use past 16 weeks without \geq 5% weight loss
 - (b) Incompatible with the stated contraindications set out in the SmPC:
- 1) A current diagnosis of uncontrolled hypertension, seizure disorder (or history of seizures), or end-stage renal failure
- 2) A history bipolar disorder, anorexia nervosa or bulimia
- 3) A current dependence on chronic opioids or opiate agonists (e.g., methadone)
- 4) A current state of acute opiate withdrawal
- 5) Any concomitant treatment containing bupropion, naltrexone, or a MAOI
- 6) Patients with a known central nervous system tumour
- 7) Patients undergoing acute alcohol or benzodiazepine withdrawal
- 8) Patients with severe hepatic impairment

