5.1	Does the protocol describe how the study exposure is defined and measured? (e.g. operational details for defining and categorising exposure, measurement of dose and duration of drug exposure)				9.3.1, 9.3.1.1
5.2	Does the protocol address the validity of the exposure measurement? (e.g. precision, accuracy, use of validation sub-study)				9.4
5.3	Is exposure categorised according to time windows?				9.3.1.1
5.4	Is intensity of exposure addressed? (e.g. dose, duration)	\boxtimes			9.3.1.1; 9.3.1.2; 9.7.4
5.5	Is exposure categorised based on biological mechanism of action and taking into account the pharmacokinetics and pharmacodynamics of the drug?		\boxtimes		
5.6	Is (are) (an) appropriate comparator(s) identified?			\boxtimes	

Comments:

- 5.2 Details of data capture reliability in each data source are covered within description of data sources.
- 5.6 This is not a comparator study, only descriptive.

Sec	tion 6: Outcome definition and measurement	Yes	No	N/A	Section Number
6.1	Does the protocol specify the primary and secondary (if applicable) outcome(s) to be investigated?	\boxtimes			8
6.2	Does the protocol describe how the outcomes are defined and measured?	\boxtimes			9.3.2, 9.7
6.3	Does the protocol address the validity of outcome measurement? (e.g. precision, accuracy, sensitivity, specificity, positive predictive value, use of validation sub-study)				9.4
6.4	Does the protocol describe specific outcomes relevant for Health Technology Assessment? (e.g. HRQoL, QALYs, DALYS, health care services utilisation, burden of disease or treatment, compliance, disease management)				
Comr	nents:				
data	Details of data capture reliability in each data source are sources.				
6.4	Study not intended for HTA submission and does not ac	ddress l	nealth e	economi	c outcomes
Sec	tion 7: Bias	Yes	No	N/A	Section Number
7.1	Does the protocol address ways to measure confounding? (e.g. confounding by indication)				
7.2	Does the protocol address selection bias? (e.g. healthy user/adherer bias)				
7.3	Does the protocol address information bias? (e.g. misclassification of exposure and outcomes, time-related bias)				
Comr	nents:				
7 Th plan	is is not a comparative study, merely descriptive; howened	ever se	nsitivity	analys	es are
Sec	tion 8: Effect measure modification	Yes	No	N/A	Section Number
8.1	Does the protocol address effect modifiers? (e.g. collection of data on known effect modifiers, sub-group analyses, anticipated direction of effect)			\boxtimes	

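### AESI incidence is to be compared by compliance status that is partly decided after index, while person-time starts at index; the false contrast depends on how often AESIs end treatment and falls mainly on the US data

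*Protocol*

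**What the plan says.** The first secondary objective in section 8 is: "To assess and compare the observed incidence of AESIs in usual clinical practice among users of Mysimba/Contrave compliant and non-compliant with the SmPC". Section 9.7.3.1 carries it out: "Incidence proportion and density of each type of AESI will also be calculated for the subgroup of patients compliant or non-compliant with the EU SmPC". For the criteria it points the reader to another place, "as listed in section 9.7.1", but section 9.7.1 deals with the timing of analyses and holds no criteria. The list stands in 9.7.2 and repeats section 8.

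Two items on that list cannot be known on the index date:

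- "Continued use past 16 weeks without" at least 5% weight loss (9.7.2 (a) 5);
- "A prescribed maintenance dose other than the Mysimba/Contrave 32mg/360mg" (9.7.2 (a) 4).

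Section 9.3.2 confirms the timing of the first: "Weight will be obtained if available 16-24 weeks post-index date to evaluate use inconsistent with labelled indication".

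Section 9.7.3 starts exposed person-time at the index date for every patient and ends it 4 weeks after the last prescription or dispensing. The denominator of the incidence proportion is all initiators. No landmark, time-varying status or index-only rule is stated, and the limitations in 9.9 do not mention the issue. Section 7 describes the focus as use "noncompliant with the Summary of Product Characteristics (SmPC) at initiation", but this is background text and removes nothing from the list.

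**The concern.** Follow-up time is attributed to a group that patients can join only by surviving and staying on drug for 16 weeks. An early AESI that kills or ends treatment keeps the patient out of the 16-week group. If the patient meets no other criterion, that event is booked as compliant. Those who do reach week 16 carry their first 112 days into the non-compliant denominator. For deaths and treatment-ending events this is immortal time. For other AESIs the fault is different: the 16-week group has at least 112 days of exposure guaranteed, which raises its incidence proportion.

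The synopsis and section 7 say that the results will inform whether the SmPC should be revised. A contrast created by the grouping rule could make non-compliant use look safer in the rates and riskier in the proportions with no true difference behind either.

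**Working it through.** The protocol states no figure for this contrast, so there is none to reproduce. The check asks what the planned calculation returns when the true ratio is 1.

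**From the protocol.** 16 weeks × 7 = 112 days (9.7.2); 4 weeks = 28 days added to exposure (9.7.3); follow-up capped at 548 days (9.2).

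**Assumed, because the protocol gives no values.** The same constant AESI hazard *h* for everyone, with events rare, so that *h* cancels; exponential time to stopping; 50% still on treatment at day 112; 15% non-compliant on baseline criteria; a share *w* = 40% or 50% of those on treatment at day 112 with less than 5% loss; a share *q* of AESIs that end treatment. The date of last prescription is treated as the stopping date.

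**Step 1, person-time per initiator.**
- Mean time to stopping: m = 112 / ln 2 = 161.58 days. Treatment is capped at 548 − 28 = 520 days.
- Mean treated days: m(1 − e^(−520/m)) = 155.11. With 28 days added: 183.11.
- Mean further treated days for those still on drug at day 112: m(1 − e^(−408/m)) = 148.65.

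**Step 2, split by group (*w* = 40%).**
- Non-compliant only through the 16-week criterion: 0.85 × 0.50 × 0.40 = 0.17 of initiators, each with 112 + 148.65 + 28 = 288.65 days, so 0.17 × 288.65 = 49.07.
- Non-compliant at baseline: 0.15 × 183.11 = 27.47.
- Non-compliant total: 76.54. Compliant: 183.11 − 76.54 = 106.57.

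**Step 3, events (in units of *h*).** The 16-week group has 0.17 × [112(1 − q) + 148.65 + 28], because treatment-ending events before day 112 cannot occur in it. Those events fall to the compliant group.
- q = 1: 0.17 × 176.65 = 30.03. Non-compliant rate (27.47 + 30.03)/76.54 = 0.751; compliant (183.11 − 57.50)/106.57 = 1.179; ratio 0.64.
- q = 0.5: 0.17 × 232.65 = 39.55. Rates 67.02/76.54 = 0.876 and 116.09/106.57 = 1.089; ratio 0.80.
- q = 0: ratio 1.00.

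**Step 4, incidence proportion.** Group shares are 0.15 + 0.17 = 0.32 and 0.68. At q = 0: (76.54/0.32) / (106.57/0.68) = 239.2/156.7 = 1.53. At q = 1: (57.50/0.32) / (125.61/0.68) = 0.97.

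| Share of AESIs ending treatment | Rate ratio, *w* = 40% / 50% | Risk ratio, *w* = 40% / 50% |
|---|---|---|
| none | 1.00 / 1.00 | 1.53 / 1.66 |
| half | 0.80 / 0.77 | 1.23 / 1.27 |
| all | 0.64 / 0.58 | 0.97 / 0.97 |

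**Checks and sensitivity.**
- A simulation without the rare-event approximation (AESI rates 10 and 50 per 1,000 person-years, 30-70% on treatment at week 16, *w* = 40%) gives rate ratios of 0.63-0.68 (all), 0.79-0.82 (half) and 0.99-1.01 (none), and risk ratios of 1.34-1.57 (none).
- If weight is recorded in only half of patients, so that the effective *w* is 20% or 25%, the same formula gives 0.76 or 0.73 (all) and 0.88 or 0.86 (half). With no weight data, *w* = 0 and every ratio is 1.00.
- If the hazard falls with time since initiation, the simulated rate ratio is 0.86 (none), 0.64 (half) and 0.47 (all).
- Compliance fixed at baseline returns 0.98-1.03 in the 15%-baseline scenarios. Splitting person-time at day 112 returns 0.99-1.01 under a constant hazard but 0.71-0.74 under a falling one.

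The maintenance-dose criterion was not modelled.

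**The case against.** **Reach.** The 16-week criterion needs follow-up weight. Appendix 3 grades weight as Partial for the US and shows no availability in the four Nordic countries; 9.3.2 warns of the same gap, and 9.7.5 bars imputed values from deciding use inconsistent with the indication. Maintenance dose is graded Maybe, for the US only. Section 9.3.1.2 assigns standard dosing where dose is missing, so those patients cannot fail that criterion. This stands: it is mainly a US problem. But 9.4.2 expects more than 20,000 US users, against a target of about 3,000 per database.

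**Which list applies.** Section 9.3.2 describes the AESI subgroup through BMI and comorbidity criteria, which can be judged at index, and the cross-reference in 9.7.3.1 is wrong. That the full 9.7.2 list governs is therefore an inference. It is the natural one, because the 9.3.2 wording is not exhaustive and no other list fits, but the sections need reconciling.

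**Descriptive intent.** Section 8 states no a priori hypotheses, and the Appendix 1 checklist (item 5.6) says "This is not a comparator study, only descriptive". No ratio or test is planned. The objective nevertheless says the groups will be compared, and rates set side by side carry the distortion without a test.

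**Stronger readings.** A reader might infer that every early AESI is booked as compliant and that the first 112 days are event-free. Neither follows. A patient who meets any other criterion is non-compliant from the start, and a non-fatal AESI with continued use stays in the 16-week group. Because 9.3.1.1 counts allowed gaps and a wash-out as use, someone who stopped shortly before day 112 may also register as past week 16. Nor does the rule always make non-compliant use look safer: with a constant hazard and no treatment-ending AESIs the rate ratio is 1.0. Taking the 16-week criterion alone, without the 28-day extension, gives ratios near 0.45 (all) and 0.70 (half), but the plan pools it with criteria that are mostly assessable at index.

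**Conclusion.** The concern holds in a conditional form. As written, the protocol classifies patients partly on what happens after index, counts their time from index, and sets the groups side by side. This is not a detail left to the SAP, since the protocol fixes both the criteria and the person-time rule.

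Under a true ratio of 1 and a constant hazard, expect a false rate ratio of about 0.6, 0.8 or 1.0 according to whether all, half or none of the AESIs end treatment, and a risk ratio of up to about 1.5-1.7 in the last case. The two planned measures can therefore disagree with no real difference present. The stopping, retention, weight-loss and baseline shares are all assumptions, and the effect shrinks as weight data go missing. The documents do not support a fixed direction of bias, or an effect of this size in the Nordic registries.

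**What to change.** In 9.7.3.1, define compliance for the AESI comparison only from criteria known at index, in line with the at-initiation wording of section 7, and align 9.3.2 with that.

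Analyse the 16-week and maintenance-dose criteria separately, in one of two ways:

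- a day-112 landmark among patients still on treatment, with events and person-time counted from the landmark; or
- time-varying status, with person-time before the criterion is met counted as not yet non-compliant and the analysis stratified by time since initiation. Splitting person-time alone is not enough if the hazard falls.

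Since weight may be taken up to week 24, state the date from which a patient is classified when the weight is recorded after day 112.

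Correct the cross-reference from 9.7.1 to 9.7.2, and reconcile the word compare in the objective with the checklist's descriptive-only statement.

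The cost is wording and person-time programming, with no new data. The downside is smaller separate tables for the post-index criteria.
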